# 1.2 Synopsis

**Protocol Title:** A Long-Term, Open Label Study to Evaluate the Ability of Tenapanor

Alone or in Combination with Sevelamer to Treat to Goal Serum Phosphorus in Patients with End-Stage Renal Disease on Dialysis

(NORMALIZE).

**Sponsor:** Ardelyx, Inc.

**Study Phase:** Phase 3

**Objectives:** The primary objective of this study is:

• To evaluate the ability of tenapanor alone or in combination with sevelamer to achieve serum phosphorus concentration (sP) within the population reference range (sP ≥2.5 and ≤4.5 mg/dL) in patients with end-stage renal disease on dialysis with hyperphosphatemia (>4.5 mg/dL).

The secondary objectives of this study are:

- To compare the phosphorus lowering effect of tenapanor and sevelamer alone in patients with sP >4.5 mg/dL to patients treated with a combination of tenapanor and sevelamer.
- To evaluate the effect of tenapanor alone and in combination with sevelamer on the proportion of patients reaching serum phosphorus targets defined as ≤4.5 mg/dL.
- To evaluate the effect of the addition of tenapanor to patients taking sevelamer on the percentage reduction in the sevelamer dose
- To evaluate the effect of tenapanor alone and in combination with sevelamer on intact fibroblast growth factor 23 (iFGF23).
- To evaluate the effect of tenapanor alone and in combination with sevelamer on the Kidney Disease Quality of Life (KDQoL) survey.
- To evaluate the effect of tenapanor alone and in combination with sevelamer on the Dialysis Symptom Index (DSI) survey (for English speakers only).
- To compare the long-term safety of tenapanor alone and in combination with sevelamer.

The exploratory objectives of this study are:

- To evaluate the effect of tenapanor alone and in combination with sevelamer on PTH, CRP, aldosterone and other cardio-renal biomarkers (These data may not be part of the study report.)
- To collect and store plasma/serum for future exploratory research into serum/plasma biomarkers related to cardio-renal disease and/or mineral metabolism or that may influence the response

Protocol No.: TEN-02-401

Edition No.: 1

(i.e. distribution, metabolism, safety, tolerability, and efficacy) to tenapanor. (These data will not be part of the study report.)

**Number of Sites:** 40-60 clinical sites in the US

Number of Patients Approximately 150-200 patients with ESRD on hemodialysis (HD) or

peritoneal dialysis (PD).

Study Design Patients who complete the TEN-02-301 study (PHREEDOM) may be

eligible to enroll into TEN-02-401 (NORMALIZE).

Patients will be required to sign an ICF and meet all inclusion/exclusion criteria. No baseline assessments will be performed as part of this protocol; all baseline data for TEN-02-401 will be taken from the TEN-02-301 End of Treatment (EOT) visit. Patients from the TEN-02-301 tenapanor arm will either receive only tenapanor or be given sevelamer in addition to tenapanor based on their sP. Patients from the TEN-02-301 sevelamer arm will be given tenapanor in addition to their sevelamer dose and the sevelamer dose will then be adjusted based on their sP following a protocol-specified dose titration schedule. Patients will be monitored for safety and efficacy with inoffice and telephone visits for up to an additional 18 months.

All study visits must be scheduled after a short dialysis interval (only for HD patients; e.g., Wednesday or Friday for patients on a MWF schedule and Thursday or Saturday for patients on a TThS schedule). Body weight and blood collections for laboratory assessments must be performed pre-dialysis. All other assessments may be performed pre-during, or post-dialysis but should be performed at the same time at each visit. For patients receiving PD, visits should be performed on the same day each week, if possible.

#### **Tenapanor Arm**

The dosing regimens described below for sevelamer are for guidance to the Investigators. Investigators have flexibility to dose sevelamer, TID, BID or QD based on their experience with each patient or as per package insert. Dosing regimens can be adjusted based on the most recent sP laboratory data (central laboratory data or standard of care local laboratory data).

If patients are in the tenapanor arm (from the TEN-02-301 study), sevelamer will be added as described below:

- $sP \ge 2.5$  and  $\le 4.5$  mg/dL: no addition of sevelamer.
- sP >4.5 and  $\leq$ 5.0 mg/dL: add one 800 mg tablet QD.
- sP > 5.0 and  $\leq 5.5$  mg/dL: add one 800 mg tablet BID.
- sP >5.5 mg/dL: add one 800 mg tablet TID.

Protocol No.: TEN-02-401

Edition No.: 1

If sP is still greater than or becomes >4.5 mg/dL at a subsequent visit, sevelamer dose can be increased in a stepwise manner as described below:

- sP >4.5 and ≤5.0 mg/dL: add one 800 mg tablet to the existing regimen.
- sP >5.0 and ≤5.5 mg/dL: add two 800 mg tablets to the existing regimen.
- sP >5.5 mg/dL: add three 800 mg tablets each day (800 mg TID) to the existing regimen.

The maximum dose of sevelamer should be based on standard of care, the sevelamer package insert, and the Investigator's experience with each patient.

If sP <2.5 mg/dL at any visit

- Sevelamer dose can be lowered by one 800 mg tablet TID, or as appropriate, based on current regimen; Investigators have flexibility to dose sevelamer BID or QD based on their experience with each patient or as per package insert.
- If patient is not taking sevelamer then tenapanor dose can be lowered by one 10 mg tablet BID, unless already at tenapanor 10 mg BID, then can dose tenapanor 10 mg QD

#### **Sevelamer Arm**

If patients are from the TEN-02-301 sevelamer arm, tenapanor dose will be added based on their baseline sP as described below. Investigators may decrease or increase the tenapanor dose based on sP levels and/or GI tolerability in 10 mg increments to a minimum of 10 mg QD or a maximum of 30 mg BID, not more than once daily. Dosing regimens can be adjusted based on the most recent sP laboratory data (central laboratory data or standard of care local laboratory data).

- sP >2.5 and ≤3.5 mg/dL: add three 10 mg tablets of tenapanor QD and Sevelamer dose can be lowered by one 800 mg tablet TID.
- sP >3.5 and  $\leq$ 4.5 mg/dL: add three 10 mg tablets of tenapanor QD
- $sP \ge 4.5$ : add three 10 mg tablets of tenapanor BID

If sP >4.5 mg/dL at next visit

- If on QD tenapanor, add three 10 mg tenapanor tablets to a maximum of 30 mg tenapanor BID. If on 30 mg tenapanor BID follow sevelamer dose regimen changes described below
- Sevelamer dose can be increased by at least one 800 mg tablet at the largest meal and up to one 800 mg tablet TID; Investigators have flexibility to dose sevelamer BID or QD based on their experience with each patient or as per package insert.

Protocol No.: TEN-02-401

Edition No.: 1

# If sP <2.5 mg/dL at any visit

- Sevelamer dose can be lowered by one 800 mg tablet TID;
   Investigators have flexibility to dose sevelamer BID or QD based on their experience with each patient or as per package insert.
- If patient is not taking sevelamer then tenapanor dose can be lowered by one 10 mg tablet BID, unless already at tenapanor 10 mg BID, then can dose tenapanor 10 mg QD

For all subjects enrolled in TEN-02-401, tenapanor will be taken either once (QD; just prior to dinner or largest meal of the day) or twice daily (BID; just prior to breakfast and dinner. Patients on HD should not take tenapanor at the meal immediately preceding dialysis; in this case, patients will take tenapanor prior to the previous or next meal after dialysis. Sevelamer will be taken as per package insert.

Investigators may decrease or increase the tenapanor dose based on sP levels and/or GI tolerability in 10 mg increments to a minimum of 10 mg BID or a maximum of 30 mg BID not more than once daily.

Laboratory assessments will be measured at every visit (Weeks 1, 2, 3, 4, 6 and 8 and Months 3, 6, 9, 12, 15 and 18) using a central laboratory.

Safety assessments will be performed during the study and will include physical examinations, vital signs (blood pressure and pulse), body weights, clinical laboratory evaluations, 12-lead electrocardiograms (ECGs), and adverse event (AE) monitoring.

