# 2.2 Description of Investigational Product

Tenapanor is a GI-acting, minimally systemic, NHE3 inhibitor. Tenapanor is administered as the hydrochloride salt and is chemically described as: (S)-N,N'-(10,17-dioxo-3,6,21,24-tetraoxa-9,11,16,18-tetraazahexacosane-1,26-diyl)bis(3-((S)-6,8-dichloro-2-methyl-1,2,3,4-tetrahydroisoquinolin-4-yl) benzenesulfonamide) dihydrochloride. Its empirical formula is  $C_{50}H_{68}Cl_6N_8O_{10}S_2$ .

Dosing consists of one to three 10 mg tablets, taken in conjunction with breakfast and dinner.

Tablets of tenapanor should be stored in the original packaging according to the labeling.

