#### 4 STUDY DESIGN

# 4.1 Design Summary

Patients who complete the TEN-02-301 study (PHREEDOM) at Visit 23, may be eligible to enroll into TEN-02-401 (NORMALIZE).

Patients will be required to sign an ICF and meet all inclusion and no exclusion criteria. No baseline assessments will be performed as part of this protocol; all baseline data for TEN-02-401 will be taken from the TEN-02-301 End of Treatment (EOT) visit. Patients from the

Protocol No.: TEN-02-401

Edition No.: 1

TEN-02-301 tenapanor arm will either receive only tenapanor or be given sevelamer in addition to tenapanor based on their sP following a protocol-specified dose titration schedule. Patients from the TEN-02-301 sevelamer arm will be given tenapanor in addition to their sevelamer dose and the sevelamer dose will then be adjusted based on their sP following a protocol-specified dose titration schedule. Patients will be monitored for safety and efficacy with in-office and telephone visits for up to an additional 18 months.

All study visits must be scheduled after a short dialysis interval (only for HD patients; e.g., Wednesday or Friday for patients on a MWF schedule and Thursday or Saturday for patients on a TThS schedule). Body weight and blood collections for laboratory assessments **must** be performed pre-dialysis. All other assessments may be performed pre-, during, or post-dialysis but should be performed at the same time at each visit. For patients receiving PD, visits should be performed on the same day each week, if possible.

Investigators may decrease or increase the dose of tenapanor based on sP levels and/or GI tolerability. The changes must be made in 10 mg increments to a minimum of 10 mg BID or a maximum of 30 mg BID. The dose of sevelamer carbonate may be adjusted based on the guidance provided in Section 4.1.1 or the sevelamer package insert. Investigators have flexibility to dose sevelamer, TID, BID or QD based on their experience with each patient or as per package insert.

Laboratory efficacy endpoints will be assessed at various times throughout the study; sP will be measured at every visit.

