#### **Sevelamer Arm**

If patients are from the TEN-02-301 sevelamer arm, tenapanor dose will be added based on their baseline sP as described below. Investigators may decrease or increase the tenapanor dose based on sP levels and/or GI tolerability in 10 mg increments to a minimum of 10 mg QD or a maximum of 30 mg BID, not more than once daily. Dosing regimens can be adjusted based on the most recent sP laboratory data (central laboratory data or standard of care local laboratory data).

- sP >2.5 and ≤3.5 mg/dL: add three 10 mg tablets of tenapanor QD and Sevelamer dose can be lowered by one 800 mg tablet TID.
- sP > 3.5 and  $\leq 4.5$  mg/dL: add three 10 mg tablets of tenapanor QD
- sP  $\geq$ 4.5: add three 10 mg tablets of tenapanor BID

If sP > 4.5 mg/dL at next visit

 add three 10 mg tenapanor tablets, if on QD regimen to a maximum of 30 mg tenapanor BID. If on 30 mg tenapanor BID follow sevelamer dose regimen changes described below.

Sevelamer dose can be increased by at least one 800 mg tablet at the largest meal and up to one 800 mg tablet TID; Investigators have flexibility to dose sevelamer BID or QD based on their experience with each patient or as per package insert. If sP <2.5 mg/dL at any visit:

- Sevelamer dose can be lowered by one 800 mg tablet TID; Investigators have flexibility
  to dose sevelamer BID or QD based on their experience with each patient or as per
  package insert.
- If patient is not taking sevelamer then tenapanor dose can be lowered by one 10 mg tablet BID, unless already at tenapanor 10 mg BID, then can dose tenapanor 10 mg QD

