#### 6.1.2 Treatments Administered

Tablets containing 10 mg of tenapanor will be taken once or twice daily PO just prior to breakfast and dinner (for QD biggest meal of the day). On dialysis days, patients on HD should **not** take study drug at the meal prior to dialysis and instead take it before another meal. Each dose of one to three tablets will achieve total daily doses between 10mg and 60 mg tenapanor. If a meal is skipped, the dose should be taken with another meal during the day or at around the time that the meal would have been consumed.

Sevelamer should be taken as described in the protocol or in the package insert.

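### The tenapanor dosing rules disagree on the minimum dose, and the sevelamer-arm starting bands overlap at sP 4.5 and omit sP of 2.5 or less

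*Combined protocol and SAP*

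**What the plan says.** **Minimum dose.** The synopsis paragraph that follows the text for all subjects lets investigators change tenapanor "in 10 mg increments to a minimum of 10 mg BID or a maximum of 30 mg BID not more than once daily". Section 4.1 (Design Summary), which covers both arms, makes this mandatory: "The changes must be made in 10 mg increments to a minimum of 10 mg BID or a maximum of 30 mg BID".

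Under the Sevelamer Arm heading, the synopsis, Section 4.1.1 and Section 6.1.3 all read "in 10 mg increments to a minimum of 10 mg QD or a maximum of 30 mg BID, not more than once daily". Section 6.1.2 adds that "Each dose of one to three tablets will achieve total daily doses between 10mg and 60 mg tenapanor".

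The rule for sP below 2.5 mg/dL, given for both arms in the synopsis, 4.1.1 and 6.1.3, lets a patient who is not on sevelamer step tenapanor down, "unless already at tenapanor 10 mg BID, then can dose tenapanor 10 mg QD". Section 2.2, a product description, mentions only twice-daily meals: "Dosing consists of one to three 10 mg tablets, taken in conjunction with breakfast and dinner".

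**Starting dose, former sevelamer arm.** Tenapanor is started according to baseline sP in three bands. The lowest is above 2.5 and up to 3.5 mg/dL (30 mg QD, with an optional sevelamer reduction). The middle is above 3.5 and up to 4.5 (30 mg QD). For the top band the dose line is "4.5: add three 10 mg tablets of tenapanor BID". The sign before that threshold is greater-than-or-equal in the synopsis and 4.1.1, and strictly greater in 6.1.3.

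**The concern.** These are the operative rules for dosing the investigational drug, and they do not agree. An investigator who takes a patient to 10 mg QD acts within 4.1.1, 6.1.2 and 6.1.3 but below the minimum in 4.1 and in the synopsis paragraph. Two investigators with a patient at a baseline sP of exactly 4.5 mg/dL could start at different doses, each following the text. A patient entering from the sevelamer arm with a baseline sP of 2.5 or less is due to receive tenapanor but has no listed starting dose.

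The stake is trial conduct and deviation reporting. Section 8.9 lists non-compliance with dosing rules as an example of a deviation. Section 11.1 says a deviation may lead to withdrawal and may make a patient non-evaluable. With 40 to 60 sites planned, the same dose could be recorded as compliant at one and as a deviation at another. The sites cannot settle this themselves, because Section 11.2 reserves changes to the sponsor. Section 9.1 gives an order of precedence only between protocol and SAP, and no provision says whether the synopsis or the body prevails.

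**Working it through.** **Step 1. Reproduce the stated daily range.** Inputs from 6.1.2: one to three 10 mg tablets per dose, once or twice daily.

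- Lowest: 1 × 10 mg × 1 = 10 mg/day.
- Highest: 3 × 10 mg × 2 = 60 mg/day.

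This matches the plan's 10 to 60 mg/day. A 10 mg BID minimum gives 1 × 10 mg × 2 = 20 mg/day, so the range would be 20 to 60. Section 6.1.2 therefore agrees with the QD minimum and not with the BID minimum.

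**Step 2. Set the minimum-dose statements side by side.**

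| Place | Minimum | mg/day |
|---|---|---|
| Synopsis, after the all-subjects paragraph | 10 mg BID | 20 |
| Section 4.1 | 10 mg BID | 20 |
| Synopsis, Sevelamer Arm | 10 mg QD | 10 |
| Section 4.1.1, Sevelamer Arm | 10 mg QD | 10 |
| Section 6.1.3, Sevelamer Arm | 10 mg QD | 10 |

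The count is two against three. The step-down for sP below 2.5 also ends at 10 mg QD in all six places where it appears (two arms × three sections).

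Ordinary titration can reach the conflict. A former sevelamer-arm patient who starts at 30 mg QD and has two 10 mg reductions, for which GI tolerability is a stated reason, arrives at 30 − 10 − 10 = 10 mg once daily. Three passages allow that dose and two do not.

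**Step 3. Test the starting bands for gaps and overlaps.** Each version was written as inequalities and evaluated at selected sP values (mg/dL).

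| Baseline sP | Synopsis and 4.1.1 | 6.1.3 |
|---|---|---|
| 2.0, 2.4, 2.5 | no band | no band |
| 2.6, 3.5 | 30 mg QD, sevelamer may be lowered | same |
| 3.6, 4.4 | 30 mg QD | same |
| 4.5 | 30 mg QD **and** 30 mg BID | 30 mg QD |
| 4.6, 5.5 | 30 mg BID | same |

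At 4.5 the two doses are 30 × 1 = 30 and 30 × 2 = 60 mg/day. Every other tested value above 2.5 falls in exactly one band.

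**Step 4. Can a patient enter with sP of 2.5 or less?** Yes. Sections 5.1 and 5.2 set no sP limit, and Section 4.1 says sevelamer-arm patients are to be given tenapanor. The separate rule for sP below 2.5 only lowers doses. It supplies no tenapanor starting dose and does not cover exactly 2.5.

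**The case against.** **The two minimums may be arm-specific.** The QD minimum does sit under Sevelamer Arm headings. But Section 4.1 restricts its minimum to neither arm, the synopsis BID sentence follows a paragraph for all subjects, and the tenapanor-arm rules also end at 10 mg QD.

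**The step-down may be a specific exception to a general minimum.** Its conditions are explicit (sP below 2.5, no sevelamer, already at 10 mg BID), so this reading is possible. No passage states it, though, and it would not explain the QD minimum in the sevelamer-arm text, which applies to any change for sP or GI tolerability.

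**The regimens are only guidance.** That wording is "The dosing regimens described below for sevelamer are for guidance to the Investigators". It concerns sevelamer and leaves the tenapanor minimum open.

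**The overlap hangs on one sign in text extracted from a PDF.** This is fair, and the sign should be checked against the PDF. Two separate sections do show the same greater-than-or-equal sign, which makes an extraction error less likely.

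**The low-end gap is softened.** The rule for sP below 2.5 applies at any visit, baseline is Visit 1, and sevelamer can be lowered there. Investigators may also adjust tenapanor by sP. This stands in part: what is missing is the tenapanor starting dose itself, and any rule at exactly 2.5.

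**The consequence is limited.** This also stands in part. Section 9.3 has no per-protocol set, and the FAS requires only eligibility, one dose and one post-baseline sP, so a dosing deviation alone removes nobody from it. That is why the claim stops at conduct and deviation reporting.

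**Conclusion.** The concern holds on all three points.

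- **Minimum dose:** 10 versus 20 mg/day. It touches only patients taken below 10 mg BID.
- **Overlap at baseline sP of exactly 4.5:** 30 versus 60 mg/day, former sevelamer-arm patients only. It assumes the printed signs in the synopsis and 4.1.1 are as extracted.
- **Low end:** any former sevelamer-arm patient with a baseline sP of 2.5 mg/dL or less has no listed tenapanor starting dose.

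None of the three can be turned into a number of patients, because the documents give no baseline sP distribution, arm split or reporting precision. Tenapanor dose is not an efficacy variable in Section 7.3, so no direct effect on the efficacy analysis is claimed. The inconsistency should be corrected because it lies in the operative dosing rules. The minimum-dose conflict is the strongest of the three, since it does not depend on a single sign.

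**What to change.** Reconcile the passages:

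1. State one tenapanor minimum in the synopsis, 4.1, 4.1.1, 6.1.2 and 6.1.3, and align the product description in 2.2 with it.
2. Say explicitly whether the step-down for sP below 2.5 is an exception to that minimum.
3. Check the sign on the top starting band against the PDF. Then make the sevelamer-arm bands mutually exclusive, exhaustive (including baseline sP of 2.5 or less) and identical in the synopsis, 4.1.1 and 6.1.3.

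Which dose and which bound are correct is for the sponsor's clinical team to decide. The cost is a clarification letter or a protocol amendment, with no added procedures or patients.

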# Patient Selection Criteria:

# **Inclusion Criteria**:

- 1. Signed and dated informed consent prior to any study specific procedures.
- 2. Completion of TEN-02-301(PHREEDOM)
- 3. Women must be non-pregnant, non-lactating and fulfilling one of the following:
  - a. Post-menopausal defined as amenorrhea for at least 12 months following cessation of all exogenous hormonal treatments and with follicle stimulating hormone (FSH) levels in the laboratory defined post-menopausal range (from TEN-02-301 study), or 60 years of age or greater.
  - b. Documentation of irreversible surgical sterilization by hysterectomy, bilateral oophorectomy or bilateral salpingectomy but not tubal ligation.

Protocol No.: TEN-02-401

Edition No.: 1

- c. Use of acceptable contraceptive method: IUD with spermicide, a female condom with spermicide, contraceptive sponge with spermicide, an intravaginal system (e.g., NuvaRing®), a diaphragm with spermicide, a cervical cap with spermicide, or oral, implantable, transdermal, or injectable contraceptives, sexual abstinence, or a sterile sexual partner.
- d. Male partner who is sterile or using a condom with spermicide.
- 4. Male participants must agree to avoid fathering a child (or donating sperm), and therefore be either sterile (documented) or agree to use, from the time of enrollment until 30 days after end of study, one of the following approved methods of contraception: a male condom with spermicide, a sterile sexual partner, use of an IUD with spermicide by female sexual partner, a female condom with spermicide, contraceptive sponge with spermicide, an intravaginal system (e.g., NuvaRing®), a diaphragm with spermicide, a cervical cap with spermicide, or oral, implantable, transdermal, or injectable contraceptives.
- 5. Able to understand and comply with the protocol.

#### **Exclusion Criteria:**

- 1. Scheduled for living donor kidney transplant, plans to change to a different method of dialysis, home HD or plans to relocate to another center during the study period.
- 2. Life expectancy <12 months.
- 3. If, in the opinion of the Investigator, the patient is unable or unwilling to fulfill the requirements of the protocol or has a condition which would render the results uninterpretable.

**Study Drug:** 

Tenapanor 10 mg tablets, and 800 mg sevelamer carbonate tablets.

# Statistical Analyses:

# **Analysis Populations:**

#### **Safety Analysis Set:**

All patients who receive at least one dose of study drug (tenapanor or sevelamer) in the study. The safety analysis set will be used for the analysis of safety variables.

